### **7.1.2      *Post-Study Treatment Study Follow-Up***

Post-study follow-up is of critical importance and is essential to preserving subject safety and the integrity of the study. Subjects who discontinue study treatment must continue to be followed for collection of outcomes and/or survival follow-up data as required and in line with Section 4 until death or the conclusion of the study.

Subjects who discontinue study treatment should be encouraged to undergo all study-related visits for the full treatment period in order to support the final efficacy and safety analysis.

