## 7.2 Discontinuation from the Study

Subjects who request to discontinue study treatment will remain in the study and must continue to be followed for protocol-specified follow-up procedures as specified in Section 1.3. The only exception to this is when a subject specifically withdraws consent for any further contact with him/her or persons previously authorized by subject to provide this information.

- Subjects should notify the investigator of the decision to withdraw consent from future follow-up **in writing**, whenever possible.
- The withdrawal of consent should be explained in detail in the medical records by the investigator and entered on the appropriate CRF page.
- In the event that vital status (whether the subject is alive or dead) is being measured, publicly available information should be used to determine vital status only as appropriately directed in accordance with local law.
- If the subject withdraws consent for disclosure of future information, the Sponsor may retain and continue to use any data collected before such a withdrawal of consent.

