### **8.2.2 Time Period and Frequency for Collecting AE and SAE Information**

The collection of nonserious AE information should begin at initiation of study treatment until discharge from the study (ie, final study visit for a given subject), at the timepoints specified in the Schedule of Activities (Section 1.3).

The Reference Safety Information in Sections 5.6.1 and 5.6.2 of the IB should be used to determine expectedness of SAEs for expedited reporting. Following the subject's written consent to participate in the study, all SAEs, whether related or not related to study drug, must be collected, including those thought to be associated with protocol-specified procedures.

All SAEs must be collected from the date of subject's written consent until 30 days after the final dose of the study drug or subject's participation in the study if the last scheduled visit occurs at a later time. Monitoring for SAEs will occur at every study visit.

- The investigator must report any SAE that occurs after these time periods and that is believed to be related to study drug or protocol-specified procedure. Medical occurrences that begin before the start of study treatment but after obtaining informed consent will be recorded on the appropriate section of the CRF.
- All SAEs will be recorded and reported to Sponsor or designee within 24 hours, as indicated in [APPENDIX 3](#).
- The investigator will submit any updated SAE data to the Sponsor within 24 hours of this being available.

Investigators are not obligated to actively seek AEs or SAEs in former study subjects. However, if the investigator learns of any SAE, including a death, at any time after a subject has been discharged from the study, and he/she considers the event reasonably related to the study treatment or study participation, the investigator must promptly notify the Sponsor.

The method of evaluating and assessing causality of AEs and SAEs and the procedures for completing and reporting/transmitting SAE reports are provided in [APPENDIX 3](#).

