## 4.2 Safety

The safety outcomes include the following:

- Adverse events (AEs)
  - Treatment-emergent adverse events (TEAEs) – defined as:
    - AEs which occur after the first dose of study treatment through 30 days after the final dose of the study treatment or subject's participation in the study if the last scheduled visit occurs at a later time.
  - Treatment-emergent adverse events of interest (AEIs) for the following events:
    - Skin-related AEs
    - Infection AEs, including influenza
    - Creatine kinase (CK) elevation (evaluated as lab toxicity grade 2 or higher)
    - Malignancy
  - SAEs
  - Deaths
- Clinical laboratory parameters
  - Absolute and change from baseline values
  - Laboratory abnormalities (as determined by Controlled Terminology Criteria for Adverse Events [CTCAE v5.0] grading) presented as the worst postbaseline toxicity group
  - Shifts from baseline to maximum postbaseline value
  - Potential drug induced liver injury (DILI) is defined as a subject who meets the following criteria:
    - 1) ALT or AST elevation >3 times ULN  
AND  
▪ 2) Total bilirubin >2 times ULN, without initial findings of cholestasis (elevated serum alkaline phosphatase)  
AND  
▪ 3) No other immediately apparent possible causes of liver function test elevation and hyperbilirubinemia, including, but not limited to, viral hepatitis, preexisting chronic or acute liver disease, or the administration of other drug(s) known to be hepatotoxic.
    - ALT or AST elevation >5 times ULN
- Vital signs
  - Absolute and change from baseline values
  - Marked abnormalities defined by the below categories:
    - Heart rate:
      - Value > 100 and change from baseline > 30
      - Value < 55 and change from baseline < -15
    - Systolic blood pressure:
      - Value > 140 and change from baseline > 20

Sponsor: Bristol-Myers Squibb

Protocol no: IM011046

- Value < 90 and change from baseline < -20
- Diastolic blood pressure:
  - Value > 90 and change from baseline > 10
  - Value < 55 and change from baseline < -10
- Electrocardiograms (ECGs)
  - Absolute and change from baseline values
  - Marked abnormalities defined by the below categories:
    - QT interval corrected using Fridericia's formula (QTcF):
      - 450 -< 480 msec
      - 480 -< 500 msec
      - $\geq$  500 msec
      - $30 < \text{change from baseline} \leq 60$  msec
      - Change from baseline > 60 msec
      - Males: < 450 msec,  $\geq$  450 msec
      - Females: < 470 msec,  $\geq$  470 msec

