## 6.0 Statistical Analyses

Descriptive summaries and analyses will be presented for data captured throughout the study using the following treatment groups.

During the first 16 weeks of treatment, summaries will be provided for the following treatment groups:

- BMS-986165 6 mg QD
- Apremilast
- Placebo

During the first 24 weeks of treatment, summaries will be provided for the following treatment groups:

- BMS-986165 6 mg QD (subjects continuously taking BMS-986165 6 mg QD)
- Apremilast

Summaries will be provided for subjects who have continuous treatment throughout the entire study with either BMS-986165 or apremilast using the following treatment groups:

- BMS-986165 6 mg QD
- Apremilast

Summaries of all subjects exposed to BMS-986165 6 mg QD will also be provided as applicable. Adverse events will be summarized using exposure-adjusted incidence rates (EAIR) for these summaries.

Please note that there will be no Chinese subjects in the apremilast group due to lack of market approval of the agent in China.

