### 6.2.1 Adverse Events

Adverse events will be presented for the number and percentage of subjects and the number of events. Treatment-emergent will be provided in listings. Summary tables will be reported in decreasing frequency based on the BMS-986165 column. Counting for frequency analysis will be by subject and not by AEs, and subjects are only counted once for recurring AEs within each system organ class (SOC) or preferred term (PT); however, the number of total AEs per subject, including multiple occurrences of individual AEs, will also be presented. For summaries of severity, AEs will be reported only at their maximum severity in each subject. Subjects with multiple AEs within a particular SOC or PT will be counted under the category of their most severe event within that SOC or PT.

AE (including deaths) dates will be imputed according to algorithms detailed in [Section 8.0](#). The imputed date of AE onset will be used to assess whether AEs should be considered as treatment-emergent and included in the safety summaries. The original, partial dates will be included in data listings. No imputation will be performed on missing AE seriousness, severity, or relationship; they will be reported as missing.

AEs will be included in a period if the start date of the AE is after the first dispensation date within a period.

An overall summary for the following categories will be presented:

- Deaths
- SAEs
- Related SAEs

Sponsor: Bristol-Myers Squibb

Protocol no: IM011046

- AEs
- Related AEs
- Discontinued treatment due to AEs

The following summaries will also be provided for the following:

- TEAEs by SOC and PT
- Treatment-related TEAEs by SOC and PT
- TEAEs by PT reported in  $\geq 5\%$  of subjects
- TEAEs by PT reported in  $\geq 1\%$  of subjects
- Treatment-related TEAEs by PT reported in  $\geq 5\%$  of subjects
- TEAEs categorized by severity by SOC and PT
- Exposure-adjusted incidence rate (EAIR) for TEAEs by SOC and PT – EAIR is defined in [Section 8.1](#) of the SAP

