Exposure-adjusted incidence rate (EAIR)	EAIR = $100 * 365.25 * (\text{total number of subjects with the AE}) / \text{total exposure time for the selected AE under each treatment}$ that a subject is exposed. Where total exposure time for each AE within a treatment is calculated as follows: 
 
• If a subject has at least 1 event while on a particular treatment, then the exposure time for that subject and AE on that treatment is: 
 
◦ First AE onset date – treatment start date (of that particular treatment) + 1
 
 
 
• If a subject does not have an event, exposure time for that AE is: 
 
◦ Treatment stop date (of that particular treatment) – Treatment start date (of that particular treatment) + 1 + 30 days (if subject discontinued or subject completed Period 3 and is not rolling into IM011075 study)
 
◦ Treatment stop date (of that particular treatment) – Treatment start date (of that particular treatment) + 1 (if subject completed Period 3 and is rolling into IM011075 study)
 
 
 
• Total exposure time = sum of exposure time for each AE within a treatment
 

First Dose Date – Study	The date a subject received their first dose on Day 1 as recorded in the eCRF Week 0 [redacted] dosing date or the earliest drug dispensation date.

Sponsor: Bristol-Myers Squibb  
Protocol no: IM011046

Last Dose Date – Study	The date of last recorded dose on the eCRF for a randomized subject.
First Dose Date – Period	The date a subject received their first dose as recorded in the eCRF Week 0 █ dosing date or the earliest drug dispensation date for Treatment Period 1 and the earliest drug dispensation date for Treatment Periods 2 and 3.
Last Dose Date – Period	The date of the last visit in the periods – 1. If a subject prematurely discontinues study treatment within a period, the date of last recorded dose on the eCRF will be used as the last dose date for the period.
Percent Change from Baseline	
Percent change from baseline is defined as ([value at post-baseline visit – value at baseline]/value at baseline) x 100.
 
If the baseline value is 0 and the post-baseline value is also 0, then the percent change from baseline is set to 0.
 
If the baseline value is 0 and the post-baseline is >0, then the percent change from baseline value will be missing.

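### SAP 8.1 does not match the EAIR event window to the at-risk window for subjects who stop drug early and stay in the study

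*SAP*

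**What the plan says.** **Events.** SAP 6.2.1 plans "Exposure-adjusted incidence rate (EAIR) for TEAEs by SOC and PT". SAP 4.2 starts the treatment-emergent window at first dose and ends it 30 days after the last dose, or at the end of the subject's "participation in the study if the last scheduled visit occurs at a later time". SAP 6.2.1 assigns events to periods by a start date only and sets no upper cut-off.

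**Time at risk.** SAP 8.1 has two rules. The first opens "If a subject has at least 1 event while on a particular treatment" and gives that subject time from treatment start to first onset, with no cap. The second covers event-free subjects. They get time on drug plus "30 days (if subject discontinued or subject completed Period 3 and is not rolling into IM011075 study"), or time on drug with nothing added if they complete and roll over. The on-treatment condition in the first rule is not defined.

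**Follow-up after stopping drug.** Protocol 7.2: "Subjects who request to discontinue study treatment will remain in the study". Protocol 7.1.2: "Subjects who discontinue study treatment should be encouraged to undergo all study-related visits for the full treatment period". Protocol 8.2.2 collects nonserious adverse events "until discharge from the study (ie, final study visit for a given subject").

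**Use.** For the summaries of all subjects exposed to BMS-986165, SAP 6.0 says: "Adverse events will be summarized using exposure-adjusted incidence rates (EAIR) for these summaries".

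**The concern.** An incidence rate needs one window: an event counts only while the subject is accruing time, and time accrues only while an event could count. Here an early stopper who stays in the study can have a countable event many months after last dose +30 days. The same subject, if event-free, stops accruing time at +30 days. Time at risk then depends on the outcome.

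At stake is the accuracy of a descriptive safety rate. EAIR is the stated adverse-event measure for the all-exposed summaries, which pool subjects with very different lengths of exposure. The error grows with the share of subjects who stop early and stay, and it need not be the same in any two groups that are set side by side.

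**Working it through.** The documents give no EAIR value, so there is no plan figure to reproduce. The check applies the SAP 8.1 rule to stated cases.

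**Inputs from the documents.** Treatment starts on Day 1. The Week 8, 16, 24 and 52 visits fall on Days 57, 113, 169 and 365, and the safety follow-up visit on Day 393. Thirty days are added for discontinued subjects and for completers who do not roll over.

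**Inputs assumed.** f is the share of an arm that stops early and stays. k is the event rate after +30 days divided by the on-drug rate. Follow-up of T = 365 days is used for simplicity.

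**Step 1, one subject.** Event-free time for a subject who stops on day s is c = s + 30.
- Stop Day 57: 87 of 365 days (24%).
- Stop Day 113: 143 of 365 days (39%).
- Stop Day 169: 199 of 365 days (55%).

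A subject who stops on Day 57 contributes 300 days if the first event is on Day 300, but 87 days if event-free to Day 365.

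**Step 2, one arm, all treatment-emergent events counted.** For a rare event, counted events are proportional to (1−f)T + f[c + k(T−c)], while counted time is about (1−f)T + fc. The relative inflation is

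f·k·(T−c) / [(1−f)T + f·c].

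Stop Day 113 (c = 143, T−c = 222), k = 1:
- f = 5%: 11.1/353.9 = 3.1%
- f = 10%: 22.2/342.8 = 6.5%
- f = 15%: 33.3/331.7 = 10.0%

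| k | f = 5% | f = 10% | f = 15% |
|---|---|---|---|
| 1 | 3.1% | 6.5% | 10.0% |
| 0.5 | 1.6% | 3.2% | 5.0% |
| 0.25 | 0.8% | 1.6% | 2.5% |
| 0 | 0 | 0 | 0 |

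At f = 10% and k = 1, moving the stop from Day 57 to Day 169 changes the inflation from 8.2% to 4.8%.

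**Step 3, check without the rare-event shortcut.** With a constant true rate of 10 per 100 patient-years, stop Day 113 and k = 1, the SAP 8.1 rule gives 10.30, 10.61 and 10.95 at f = 5%, 10% and 15%. Matched windows give 10.00 each time. Two groups with equal true rates but f of 5% and 15% would show a ratio of 10.30/10.95 = 0.94. At k = 0.5 the ratio is 0.97, and at k = 0.25 it is 0.98.

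**Step 4, different assumptions.** Let 10–30% of subjects stop, with stop days uniform over Days 1–364. Let 25–100% of them stay to Day 393, with the same rate on and off drug. For true rates of 1 to 50 per 100 patient-years the inflation runs from 0.9% to 15.8%. The top figure needs 30% stopping and all of them staying.

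**Step 5, the other reading.** If only on-drug events count, the added 30 days cannot yield an event. They make up 30/395 = 7.6% of the time of an event-free completer who does not roll over, and 30/143 = 21% for a Day 113 stopper. If 75% of completers roll over (assumed), they are 0.25×30/(365 + 0.25×30) = 7.5/372.5 = 2.0% of completers' time. The bias is then downward.

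**Step 6, completers.** Day 365 + 30 = Day 395, against a nominal last visit on Day 393 (±3 days). The difference is about two days and does not matter.

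**The case against.** The strongest reply is that a third reading matches the windows. SAP 8.1 is written per treatment, and its event-free rule ends at stop +30 days. The first limb of the SAP 4.2 definition also ends at +30 days. If being on a treatment means that same interval, numerator and denominator agree. This may well be the intent, but neither document says so, and SAP 6.2.1 applies EAIR to treatment-emergent events, whose definition has the later limb. Both readings that follow directly from the text leave the windows unmatched.

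Several stronger inferences are tempting but not supported:
- *Early stoppers add events without time.* They do not. A subject with a late event contributes time to onset; what is lost is the observed time after +30 days in those who stay event-free.
- *Every event-free subject's time runs to +30 days.* Rollover completers get nothing added.
- *The bias is known to be upward.* Its direction turns on the undefined on-treatment condition.
- *All early stoppers are followed to the end.* Protocol 7.1.2 encourages attendance. How many stay for months is unknown, and the upward bias exists only to the extent that they do.
- *Treatment comparisons are distorted.* SAP 6.0 ties EAIR mainly to the pooled all-exposed summary, and SAP 6.2.1 names no comparative EAIR table. The 5% against 15% contrast is an illustration, not a forecast.

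The reply is also right that planned counts and percentages of subjects with events are unaffected.

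**Conclusion.** The point holds as a definition that gives an inaccurate rate for one group: subjects who stop drug early and remain under adverse-event collection. If all treatment-emergent events count, the bias is upward, about 1–10% per arm for a Day 113 stop, f of 5–15% and k of 0.25–1, and zero if there are no late events. If only on-drug events count, it is downward. The documents supply neither f nor k, so the size is a range under assumptions, not an estimate. Rollover completers and the Week 56 difference are not material. EAIR is descriptive: no test, efficacy conclusion or crude adverse-event table changes. Severity is the lowest.

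**What to change.** Add one rule to SAP 8.1: an event counts in the EAIR only if its onset lies in the interval used for event-free subjects. That interval runs from treatment start to the earliest of last dose +30 days, last contact, and first dose of the next study treatment. For rollover subjects it ends at treatment stop, as now. Define the on-treatment wording in SAP 8.1 as this interval, and apply the same end date to event-free time. Leave SAP 4.2 and the treatment-emergent event tables unchanged, and list later events in early stoppers separately.

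The cost is one sentence and one onset-date condition in the EAIR program, settled before database lock. No visit or collection rule changes. The downside is that events beyond last dose +30 days leave the EAIR; they remain in the treatment-emergent tables and in the separate listing.

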**Table 2: On Treatment Procedural Outline (IM011046): Week 0 through Week 20**

Procedure	Week 0 Baseline/D1 V2	Week 1 D8 (±3 d) V3	Week 2 D15 (±3 d) V4	Week 4 D29 (±3 d) V5	Week 8 D57 (±3 d) V6	Week 12 D85 (±3 d) V7	Week 16 D113 (±3 d) V8	Week 20 D141 (±3 d) V9	Notes
Hematology	X	X	X	X	X	X	X	X	
Lymphocyte Subsets (TBNK)	X				X		X		
Chemistry Panel	X	X	X	X	X	X	X	X	If CK >2.5 × ULN, reflex testing is required (see Section 8.4.5)
Hemoglobin A1C	X						X		
hs-CRP	X	X	X	X	X		X	X	
Fasting Lipid Panel	X				X		X		
Fasting Plasma Glucose	X				X		X		
Urinalysis	X						X		
Serum Immunoglobulin Levels (IgM, IgG, IgA, IgE)	X				X		X		
Pregnancy Test (Urine)	X			X	X	X	X	X	WOCBP only
Study Treatment									
Randomize	X								
Dispense Study Treatment	X		X	X	X	X	X	X	
Study Treatment Compliance		X	X	X	X	X	X	X	See Section 6.6

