### **Apremilast:**

For subjects randomized to apremilast, the Week 24 date will be used as the date of last dose of apremilast and the date of first dose of either apremilast or BMS-986165 for the subsequent period. Subjects who receive apremilast at Week 24 through to Week 52 will be counted as a sum of the first 24 weeks of treatment and the next treatment period.

- Apremilast (Wk 0 through Wk 24) = Week 24 date – date of first dose +1
- Apremilast (Wk 24 through Wk 52) = Date of last dose – Week 24 date
- Total Apremilast = Duration of apremilast Wk 0-24 + duration of apremilast Wk 24-52
- BMS-986165 = Date of last dose of BMS-986165 – Week 24 date

Total apremilast duration of treatment will be displayed as well as BMS-986165 treatment duration. If subject discontinues their study treatment during the initial 24 weeks of apremilast treatment, the date of last dose will be used as the duration of apremilast.

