#### **6.3.4.3 Compliance**

Treatment compliance will be determined from data captured on the Drug Accountability eCRF.

*Number of expected doses: (date of next visit – date of current visit) x 3*

[figure not shown]
Treatment compliance will be derived for each period. Compliance is defined as:

$$\left( \frac{\text{Number of doses taken}}{\text{Number of expected doses}} \right) \times 100$$

Period compliance will be calculated by summing over all visits within the period using descriptive statistics by treatment group. The number and percentage of subjects with <75%, 75% to 100%, and >100% compliance will be provided by treatment group for each period. If a subject does not return the container, then this dispensation event will be excluded in the calculation for the total number of doses taken, total number of expected doses, and total compliance.

Sponsor: Bristol-Myers Squibb

Protocol no: IM011046

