## 8.4 Study Periods

Period 1 = Week 0 to Week 16 visit date

Period 2 = Week 16 visit date +1 to Week 24 visit date

Period 3 = Week 24 visit date +1 to Week 52 visit date

Follow-up = 4 week follow-up period

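### Read literally with SAP 8.4, the adverse-event rule in SAP 6.2.1 opens Periods 2 and 3 about 28 days after each switch to BMS-986165

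*SAP*

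**What the plan says.** SAP 8.4 defines three adjoining periods: "Period 1 = Week 0 to Week 16 visit date", then "Period 2 = Week 16 visit date +1 to Week 24 visit date", then "Period 3 = Week 24 visit date +1 to Week 52 visit date". The Week 16 and Week 24 visit dates therefore belong to the earlier period.

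Both are dispensing visits. The row "Dispense Study Treatment" in protocol Table 2 is marked at Weeks 16 and 20, and the same row in Table 3 at Weeks 24 and 28. Placebo subjects switch to BMS-986165 at Week 16. Apremilast subjects without a PASI 50 response switch at Week 24.

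Four other SAP rules depend on where a period begins:

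- 6.2.1, AE assignment: "AEs will be included in a period if the start date of the AE is after the first dispensation date within a period". No end date is given.
- 8.1, first dose date of a period: "the earliest drug dispensation date for Treatment Periods 2 and 3". The last dose date of a period is its last visit minus one day.
- 6.3.4.1, apremilast duration by group: "the Week 24 date will be used as the date of last dose of apremilast and the date of first dose" of the following treatment.
- 6.3.4.3, compliance: "Period compliance will be calculated by summing over all visits within the period".

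SAP 8.5 lists the Week 16 analysis visit in Period 1 and the Week 24 visit in Period 2. It starts the next visit window on the day after the Week 16 or Week 24 dispense date.

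**The concern.** The tablets that start Period 2 are handed out on a date that 8.4 assigns to Period 1, and the same happens at Week 24. A programmer who combines 8.4 with the word *within* in 6.2.1 finds the first dispensation of Period 2 at Week 20 and of Period 3 at Week 28. The AE windows then open about four weeks after the treatment change.

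Those weeks are the first exposure to BMS-986165 for every placebo switcher and every apremilast switcher, when early events on a new drug would be looked for. Because 6.2.1 has no end date, the text does not say what becomes of these events. If 8.4 closes the earlier period, they drop out of the by-period tables. If nothing closes it, they stay in the earlier period and may be shown under placebo or apremilast. The period rule is not limited to switchers, so continuing subjects lose the same days in any table built from period flags.

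**Working it through.** The plan states no period length or gap, so there is no figure to reproduce. The check is day arithmetic on the nominal schedule.

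**Inputs.** Protocol Tables 2 and 3: Week 16 = Day 113, Week 20 = Day 141, Week 24 = Day 169, Week 28 = Day 197, Week 52 = Day 365, each ±3 days. SAP 8.4 windows: Days 1-113, 114-169 and 170-365. SAP 8.1 last dose dates: Days 112, 168 and 364. Duration by period (SAP 6.3.4.1) = last dose − first dose + 1.

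**Step 1: AE windows, literal reading.** The first dispensation inside Days 114-169 is Day 141, and inside Days 170-365 it is Day 197. AEs must start after those dates, so the windows open on Days 142 and 198. The onset days missed are:

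- after Week 16: Days 114-141, 141 − 114 + 1 = 28 days
- after Week 24: Days 170-197, 197 − 170 + 1 = 28 days

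Each gap runs between two visits that may each move by 3 days, so it can be 28 − 6 = 22 to 28 + 6 = 34 days.

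**Step 2: exposure by period, two readings of 8.1.**

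| | Period 1 | Period 2 | Period 3 | Total |
|---|---|---|---|---|
| First dispensation inside the 8.4 window | 112 − 1 + 1 = 112 | 168 − 141 + 1 = 28 | 364 − 197 + 1 = 168 | 308 |
| Dispensation that supplies the period | 112 | 168 − 113 + 1 = 56 | 364 − 169 + 1 = 196 | 364 |

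The first reading leaves out Days 113-140 and 169-196: 2 × 28 = 56 = 364 − 308. The second leaves no gap.

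**Step 3: AE windows if the Week 16 and Week 24 dispensations open the periods.** The windows, closed at the 8.4 end dates, are Days 2-113, 114-169 and 170-365. Neither switch leaves a gap. Only Day 1 is uncovered, because 6.2.1 requires a start after the dispensation date.

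**Step 4: compliance.** Expected tablets are (next visit − current visit) × 3. Weeks 0-16 give (113 − 1) × 3 = 336. Week 16 is a Period 1 visit under 8.4, so summing over visits in the period adds (141 − 113) × 3 = 84, for a total of 420. If that sum were used for the 75% cut in SAP 5.1:

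- 0.75 × 420 = 315. A subject who takes all 84 tablets in Weeks 16-20 needs 315 − 84 = 231 before Week 16, and 231/336 = 68.75%.
- A subject at 90% before Week 16 who returns the Week 16 kit unused scores 0.90 × 336 / 420 = 72%.

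**The case against.** A reader might infer that four weeks after each switch belong to no period. SAP 8.4 rules that out: its windows adjoin and cover every day from 1 to 365. The days can fall outside an AE or dose window, but not outside the periods.

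The better defence is that the authors meant the Week 16 and Week 24 dispensations throughout. SAP 8.1 says *for* Periods 2 and 3, not *within* them. On that reading the last-dose rule meets the next first dose exactly (Days 112/113 and 168/169), and 112 + 56 + 196 = 364. SAP 8.5 also uses the Week 16 and Week 24 dispense dates as the hinge. This stands for exposure and is probably the intent. It does not remove the conflict, because the first dose date then lies in the period that 8.4 has just closed, and 6.2.1 still says *within*.

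Nor do the documents show that early switcher events vanish from safety reporting. Treatment-emergent status in SAP 4.2 makes no use of periods. The exposure-adjusted rates in 8.1 run from the start of each particular treatment, and SAP 6.0 plans them for all subjects exposed to BMS-986165. That section also names no separate Period 2 or Period 3 switcher group. All of this stands. Still, SAP 6.2 presents safety by period and treatment group as applicable, and protocol 9.5 lists a placebo-to-BMS-986165 group after Week 16. For placebo switchers, 6.3.4.1 relies on a first BMS-986165 dose date that it does not define further.

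It is also tempting to conclude that the per-protocol set is misclassified. SAP 5.1 sets its own window, the first 16 weeks of treatment, and on its terms the Week 16 kit does not count. What remains is a mismatch with 6.3.4.3, which derives compliance only by period. The difference in 6.3.4.1, where the Week 24 date is both last and first dose, is one day and belongs to duration by group, a separate summary.

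**Conclusion.** The inconsistency is real and should be corrected. As written, 6.2.1 and 8.4 together leave the first 28 nominal days after each switch (22 to 34 with visit windows) outside the new period's AE window, and do not say whether those events are dropped or kept under the earlier treatment.

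The exposure shortfall of 28 against 56 days and 168 against 196 days is conditional: it follows only if 8.1 is read as the first dispensation inside the 8.4 window. The 68.75% and 72% compliance examples apply only if the Period 1 sum is used in place of the window in 5.1.

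This rests on dispensing at every scheduled visit, on nominal visit days, and on 8.4 supplying the windows for 6.2.1. The coprimary analysis is untouched. The consequence is confined to by-period AE and exposure summaries and to the compliance figure.

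**What to change.** Make these wording changes in the SAP:

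- **8.1 and 6.2.1:** state that the Week 16 and Week 24 dispensing dates are the first-dose dates of Periods 2 and 3, for dosing and for AE assignment.
- **6.2.1:** give the AE rule an end date, namely the next period's first-dose date, and a same-day convention. One that fits 8.4 keeps an onset on the Week 16 or Week 24 dispensing date in the earlier period and puts a treatment-emergent onset on Day 1 in Period 1.
- **8.4 and 8.5:** keep the present boundaries for assessments. Ending each period the day before dispensing would move the Week 16 and Week 24 assessments, including the coprimary endpoints, out of the periods where 8.5 lists them.
- **6.3.4.3:** state that Period 1 compliance sums dispensations from Week 0 up to but not including Week 16, in line with 5.1.

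The cost is a few sentences and a change to the derivation of the period flags. No new data are needed.
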